10.5 Statistical Considerations and Data Analysis

The primary objective of this study is to investigate whether fertility treatment is associated with changes in the **prevalence** and **severity** of Irritable Bowel Syndrome (IBS) symptoms. Specifically, the study aims to:

3. Assess whether the **proportion of participants meeting IBS diagnostic criteria** (based on ROME III and IV) differs **before and after fertility treatment**.
4. Evaluate whether there is a **statistically significant change in IBS symptom severity** as measured by the **IBS Symptom Severity Score (IBS-SSS)** before and after treatment.
5. Identify which **psychological and clinical factors** are associated with the presence or change in IBS symptoms in women undergoing fertility treatments, including those with **Polycystic Ovary Syndrome (PCOS)** and those undergoing **social oocyte freezing**.

Participants will either meet the criteria for IBS or not meet the criteria for IBS (based on the ROME III and IV criteria). This will correlate to a binary outcome: yes (1) or no (0) answer. This answer will be defined before and after the fertility treatment. A logistic regression model will be used to determine the chance of P(1) which is the chance of meeting the IBS criteria (yes answer). This regression model will be used for the PCOS group and the social freezing group. This model estimates the probability of an event occurring (meeting the IBS criteria) based on a given set of independent variables. The independent variables include GAD-7 score, PHQ-9 score, ethnicity, duration of the desire to have children, the number of follicles found on the US,...

These independent variables will be evaluated with the AIC (Akaike information criterion). AIC is used to compare different possible regression models and define which model is the best fit for the given data. If the AIC is lower, the data is a better fit. The regression model will be made with different independent variables and each time the AIC will be calculated. The model with the lowest AIC will be the final model.

Participants will fill in the IBS-SSS and obtain a score between 0 and 500. The difference in score before and after the fertility treatment will be calculated. This score difference, which is a continuous outcome, will be used in a multiple linear regression model. This model estimates how several independent variables influence a single outcome. The regression analysis will show which independent variables (such as ethnicity, anxiety scores, duration of the desire to have children,...) have an influence on the score difference of IBS-SSS questionnaire. AIC will be used to evaluate the different possible models which will include different independent variables. The model with the lowest AIC will be used.

All analyses will be performed with SPSS.

11 Ethical Considerations

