6.1.1 Primary research hypotheses

H1.

The prevalence of participants meeting diagnostic criteria for Irritable Bowel Syndrome (IBS), as defined by the ROME III and ROME IV criteria, differs significantly before and after fertility treatment.

H2.

IBS symptom severity, as measured by the IBS Symptom Severity Score (IBS-SSS), changes significantly following fertility treatment compared with baseline.

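### Section 10.5 restates the primary aims as before/after contrasts but states only models for associated factors: none tests a change in prevalence (H1), and the mean change in IBS-SSS (H2) is never named as a quantity to estimate or test

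*Protocol*

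**What the plan says.** Protocol section 6.1.1 sets two primary hypotheses. H1 is that the share of women with IBS, "as defined by the ROME III and ROME IV criteria, differs significantly before and after fertility treatment". H2 is that "IBS symptom severity, as measured by the IBS Symptom Severity Score (IBS-SSS), changes significantly following fertility treatment compared with baseline". Sections 4 and 6.3 say that these outcomes will be compared before and after treatment, but name no test.

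Section 10.5 repeats the two contrasts as its items 3 and 4 and adds item 5, the search for associated psychological and clinical factors. Two models follow.

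- **Binary outcome.** Each woman has a yes/no answer on the IBS criteria: "This answer will be defined before and after the fertility treatment". The stated analysis is: "A logistic regression model will be used to determine the chance of P(1) which is the chance of meeting the IBS criteria (yes answer". On predictors: "The independent variables include GAD-7 score, PHQ-9 score, ethnicity, duration of the desire to have children, the number of follicles found on the US", and the list is left open. On selection: "The model with the lowest AIC will be the final model".
- **IBS-SSS.** "The difference in score before and after the fertility treatment will be calculated". Then: "This score difference, which is a continuous outcome, will be used in a multiple linear regression model". The stated purpose is to show which variables influence the difference, and AIC again chooses the model.

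**The concern.** H1 and H2 ask whether the same women differ after stimulation from how they were before. The logistic model asks which women meet the IBS criteria. The linear model asks which women change more than others. Both questions belong to item 5, the secondary objective.

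This is more than detail left for a statistical analysis plan. Section 10.5 names the primary contrasts and then commits to analyses of something else. An analyst following it would report predictors of IBS and predictors of change, with no test or interval for the change in prevalence and no stated test of the mean change in severity. The paired test would then be chosen after the data are in, along with the Rome definition and the population.

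**Working it through.** The protocol gives no calculated figure to reproduce: the target of 120 follows the size of an earlier study, and no alpha, power or effect size is stated. The check compares what each hypothesis needs with what each model contains. All numerical settings below are assumptions unless a section is cited.

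**1. H1 and the logistic model.** H1 needs a parameter for after minus before. Section 10.5 leaves three ways to fit the model:

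- *One visit only.* The other answer is unused and there is no contrast.
- *Each visit separately.* Each fit reproduces that visit's observed proportion on average, so the two proportions can be read off. No coefficient, interval or test compares them.
- *Both visits stacked.* Without a visit term there is still no contrast. If one is added through the open list, AIC may drop it, and two answers per woman are treated as two women.

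None of the three tests H1 as written.

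**2. Size of the stacking error (illustration only).** With equal variance σ² at both visits and within-woman correlation ρ, the variance of the before/after difference is 2σ²/n if the visits are treated as independent and 2σ²(1−ρ)/n if paired. The SE ratio is 1/√(1−ρ). At ρ = 0.5 it is 1/√0.5 = 1.41, so the SE of the change is overstated about 1.41 times.

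**3. H2 and the linear model.** The outcome is the within-woman difference, so pairing is kept. H2 is the statement that its mean is not zero. A slope says how the difference varies with a covariate. The uncentred intercept is the expected difference for a woman at zero or reference on every covariate. Only with mean-centred covariates does the intercept equal the mean change.

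Simulation: 2000 runs, 120 women, GAD-7 normal with mean 7 and SD 4, duration normal with mean 2 and SD 1.5, residual SD 80, two-sided 5% level.

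| True state | Mean-centred intercept | Uncentred intercept | GAD-7 slope |
|---|---|---|---|
| Mean change 40, no covariate effect | 99.95% | 59% | 5.8% |
| Mean change 0, 8 points per GAD-7 point | 7% | 87% | 98.8% |

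In the first row a clear mean change leaves the slope at about its nominal error rate. In the second row there is no mean change, yet the uncentred intercept rejects in 87% of runs because it estimates 8 × (0 − 7) = −56 points.

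The 7% is slightly above 5% because the centred intercept's SE omits the spread due to the covariate. The total variance is 80² + (8 × 4)² = 7424 against 6400, an SE ratio of √(7424/6400) = 1.08. A paired t interval uses the full spread.

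**4. What a paired analysis would give.** Exact McNemar p-values are 2 × 0.5⁵ = 0.0625 for 5 against 0 switches and 2 × 0.5⁶ = 0.031 for 6 against 0. Take the background Rome IV prevalence of 3.8% (sections 5.6 and 9.3.1), a rise to 10%, 0% to 2% of women switching from yes to no, two-sided alpha 0.05 and no dropout. Power is then 0.16–0.17 with 60 women and 0.48–0.76 with 120. For H2, the smallest standardised mean change with 80% power is (1.96 + 0.84)/√n: 0.36 with 60 and 0.26 with 120. The choice of per group or pooled therefore matters.

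**The case against.** **The H2 model is usable.** This stands in part. A reader might infer that neither hypothesis can be estimated from the stated models. For H2 the documents do not support that: the difference is formed within each woman, and a least-squares fit evaluated at the covariate means returns the mean change. The gap is that the contrast is unnamed and no centring is stated.

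**The predictor lists are open, and stacking is nowhere described.** Correct. A visit term is unstated, not excluded, so the 1.41 illustrates one possible reading and does not describe the plan. A reader might also assume a correlation well above 0.5 and a larger error. For binary answers with prevalences p₁ < p₂ the correlation cannot exceed √[p₁(1−p₂)/((1−p₁)p₂)]. That is √(0.038 × 0.90/(0.962 × 0.10)) = 0.60 for 3.8% to 10%, and √(0.101 × 0.80/(0.899 × 0.20)) = 0.67 for 10.1% to 20%. Higher values need prevalence to change little.

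**The intercept might be said to describe a woman with no follicles.** Follicle count is named for the logistic model. The linear model's own list does not name it, so that example should not be used.

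**The study is exploratory, and an analysis plan may add paired tests.** Both may be so. But H1 and H2 are worded as significant change, and section 10.5 already commits to models that address another aim.

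**McNemar does not rescue H1.** Rome IV asks about the last 3 months and requires onset at least 6 months earlier (section 9.3.1), so new IBS during stimulation may hardly register. That is a separate question about the endpoint and does not excuse the missing contrast.

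**Conclusion.** The point holds in this form. For H1, following section 10.5 as written yields no test or interval for the change in prevalence. This rests on the text alone. For H2, the pairing is kept and the mean change is recoverable, but the stated analysis looks only for predictors of the difference. Its slopes do not test the mean change, and its uncentred intercept can mislead.

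The simulation rates depend on the assumed SD, slope and covariate distributions. They show that the quantities differ, not what this study will find. The 1.41 depends on stacking, an added visit term, equal variances and an assumed correlation of 0.5. The data are not at fault: sections 9.2.2 and 9.2.3 collect the questionnaires at both visits. Because both primary hypotheses are affected, the text should be corrected before analysis.

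**What to change.** In section 10.5:

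- **H1:** state the paired difference in proportions with 95% CI and an exact McNemar test, separately for Rome III and Rome IV. Name one definition and one population (pooled or per group) as primary. Two definitions by three populations (PCOS, social freezing, pooled) would otherwise give six candidate tests.
- **H2:** state the mean paired IBS-SSS change with 95% CI by paired t, with the Wilcoxon signed-rank test as sensitivity analysis. Name the primary population here too.
- **Associated factors:** keep the AIC-selected regressions for this secondary objective only, and say which visit's answer the logistic model uses. If both visits enter one model, use GEE or a mixed model clustered on woman, with the visit term forced in and outside AIC selection.

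The cost is a short paragraph and a decision on the primary definition and population. The data are already planned, and the methods are standard SPSS procedures.

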
Target sample size:
	
Since there is no study that has explored the prevalence of IBS during a fertility treatment, there is not enough data to do a power analysis before starting this study. This study will be an explorative study with a PCOS group of 60 and social freezing group of 60. After the data has been collected, a power analysis will be done and the option of including more participants will be explored. In this case, we will submit an amendment to the ethical committee.
 
There are multiple studies that found a connection between IBS and infertility. Most of these studies are retrospective studies and are focused on male infertility. (1). A study in 2013 analyzed gastro-intestinal symptoms during IVF in infertile women. This study had 124 participants. (2) Since this study from 2013 is the most like our study, the aim for our target sample size is going to be similar, namely 120 participants.

5 Background and Rationale

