6.2.1 Secondary research hypotheses

H3.

Changes in depressive symptom levels are significantly associated with changes in IBS symptom severity in women undergoing fertility treatment.

H4.

Changes in anxiety levels are significantly associated with changes in IBS symptom severity in women undergoing fertility treatment.

H5.

Changes in IBS symptoms differ significantly according to the type of ovarian stimulation used during fertility treatment.

H6.

Changes in IBS symptoms differ significantly based on the number of fertility treatments received prior to the current treatment.

H7.

Changes in IBS symptoms differ significantly according to the duration of infertility.

H8.

The prevalence and/or change in IBS symptoms differ significantly across ethnic groups.

H9.

Among women with Polycystic Ovary Syndrome (PCOS), changes in IBS symptoms differ significantly according to PCOS phenotype.

H10.

Changes in IBS symptoms are significantly associated with the hormonal profile during controlled ovarian stimulation (COS).

H11.

Changes in IBS symptoms differ significantly according to the ovarian response assessed by ultrasound during COS.

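### H3 and H4 are separate association hypotheses, but section 10.5 addresses them only through a lowest-AIC model, which can drop a truly associated scale and leave its hypothesis without an estimate

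*Protocol*

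**What the plan says.** Protocol section 6.2.1 lists two separate secondary hypotheses. The depression hypothesis, H3, reads: "Changes in depressive symptom levels are significantly associated with changes in IBS symptom severity in women undergoing fertility treatment". The next one, H4, makes the same claim for anxiety. Each concerns a change score and an association with change in IBS severity.

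Section 10.5 describes two regressions.

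- **Logistic model for meeting the IBS criteria.** "The independent variables include GAD-7 score, PHQ-9 score, ethnicity" and further items form one candidate set, and "The model with the lowest AIC will be the final model".
- **Linear model for the before–after IBS-SSS difference.** "This score difference, which is a continuous outcome, will be used in a multiple linear regression model". The reading of the result is stated as follows: "The regression analysis will show which independent variables (such as ethnicity, anxiety scores" and further examples) influence the difference. Anxiety scores are named there. PHQ-9 is not, but the list is given only as examples. Selection is again by AIC: "The model with the lowest AIC will be used".

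The protocol summary (section 4, target sample size) gives the numbers: "This study will be an explorative study with a PCOS group of 60 and social freezing group of 60". Section 10.5 does not say whether the linear model is fitted per group (n = 60) or pooled (n = 120).

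**The concern.** H3 and H4 ask whether each scale, taken by itself, is associated with IBS-SSS change. Lowest-AIC selection asks whether a scale improves prediction given whatever else is in the model. When two predictors are correlated these are different questions. A scale can be truly associated with the outcome and still be dropped because the other scale already carries most of its information.

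Section 10.5 does not require the PHQ-9 change or the GAD-7 change to stay in the model, and does not say how a dropped variable will be reported. Following the plan as written can therefore leave H3 or H4 with no estimate and no interval. Because the regression is said to show which variables influence the score difference, absence from the final model is liable to be taken as absence of association. The secondary objective, identifying which psychological factors go with IBS change, would then get an incomplete and unstable answer. Correcting p-values for the model search would not bring back a missing estimate.

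**Working it through.** **The plan's own figure.** There is none to reproduce. The protocol gives no effect size, power or correlation for this question.

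**Inputs**

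- From the protocol: n = 60 per group, or 60 + 60 = 120 pooled; linear regression of the IBS-SSS difference; lowest AIC wins.
- Assumed: correlation ρ between GAD-7 change and PHQ-9 change of 0.5 to 0.8; equal marginal correlation m of each with IBS-SSS change, 0.3 or 0.4; normal data.
- Support for some overlap in the appendices: both scales use a two-week recall and 0–3 frequency responses, and both touch on restlessness (GAD-7 item 5, and part of PHQ-9 item 8). Section 9.2 has them completed at the same visits. None of this fixes the size of ρ.

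**Step 1: what AIC requires.** Adding the second scale lowers AIC when n·ln(S1/S12) > 2, where S1 and S12 are the residual sums of squares with one and with both scales. In terms of the added term, |t| > sqrt[(exp(2/n) − 1)(n − 3)]. This is 1.39 at n = 60 and 1.40 at n = 120.

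**Step 2: what the second scale delivers.** Its partial correlation is m(1 − ρ)/sqrt[(1 − m²)(1 − ρ²)]. With m = 0.3 and ρ = 0.7:

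- 0.09/sqrt(0.91 × 0.51) = 0.13.
- Typical t at n = 60: 0.132 × sqrt[57/(1 − 0.132²)] = 1.0, below 1.39.
- Typical t at n = 120: about 1.44, close to the 1.40 threshold. Keeping both scales requires each to clear the threshold given the other.

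**Step 3: how often exactly one is kept.** Four candidate models (neither, GAD-7 only, PHQ-9 only, both), 4,000 data sets per setting, both scales truly and equally associated with the outcome:

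| n | m | ρ = 0.5 | ρ = 0.6 | ρ = 0.7 | ρ = 0.8 |
|---|---|---|---|---|---|
| 60 | 0.3 | 76% | 82% | 86% | 87% |
| 60 | 0.4 | 52% | 69% | 84% | 94% |
| 120 | 0.3 | 52% | 68% | 83% | 94% |
| 120 | 0.4 | 15% | 30% | 54% | 79% |

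A version with three irrelevant extra candidates and all 32 subsets gave nearly the same figures: 74–87% (n = 60, m = 0.3), 52–94% (n = 120, m = 0.3) and 51–93% (n = 60, m = 0.4).

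**Step 4: comparison with separate models.** At n = 60, a model containing one scale gives |t| > 2 for that scale in about 65% of data sets at m = 0.3 and about 90% at m = 0.4, almost regardless of ρ. At ρ = 0.7 the lowest-AIC rule keeps both in only 6% and 15%. Among data sets at n = 60 and ρ = 0.7 in which both scales were significant on their own, AIC still dropped one in 92% (m = 0.3) and 83% (m = 0.4).

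**The case against.** **The size depends on unstated quantities.** This stands. A reader might infer that the two scales overlap strongly and that AIC will usually keep only one. The protocol gives no correlation, and a shared recall period and response format do not establish one. PHQ-9 also covers sleep, appetite and fatigue, which GAD-7 does not ask about directly. H3 and H4 moreover concern changes, whose correlation is equally unknown. At n = 120 and m = 0.5, exactly one scale is kept in only 2–46% of data sets; with uncorrelated scales at n = 60 the share is 0–23% for m from 0.5 down to 0.3.

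**The explicit listing of both scales belongs to the logistic model.** This also stands. H3 and H4 concern severity, hence the linear model, where PHQ-9 is not named. That both compete there is a reading of an open-ended list. It does not rescue the plan: if PHQ-9 were left out of the linear model, H3 would have no analysis in section 10.5.

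**Nothing says a dropped scale will be reported as having no influence.** Correct. That is a likely misreading, not a planned statement.

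**Dropping a redundant scale can be right.** For a conditional question, yes. With ρ = 0.7, a unique effect of 0.4 for one scale and none for the other, AIC at n = 60 keeps only the first in 77% of data sets. But the second then still has a marginal correlation of 0.4 × 0.7 = 0.28 with the outcome, and H3 and H4 are worded marginally. The idea that the choice between the scales is a coin toss holds only when their associations are about equal.

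**H10 and H11.** One might extend the point to hormones and follicle count. The documents do not say how these move together, and section 10.5 does not name the hormonal profile among its candidates, so the extension is not supported.

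**The study is explorative, and covariate sets may sit in a statistical analysis plan.** True, but the protocol itself fixes the selection rule, and exploration needs every estimate to be visible.

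**Conclusion.** The concern holds in conditional form. Section 10.5 offers H3 and H4 only a lowest-AIC model, with no forced inclusion and no estimate promised for a dropped scale, and that rule does not answer the associations as worded.

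How often this bites depends on assumptions the protocol does not supply. With a correlation of 0.5 to 0.8 between the two changes and equal true associations, one scale is lost in about 75–87% (n = 60) or 52–94% (n = 120) of data sets at an association of 0.3, and in 52–94% or 15–79% at 0.4. With weaker overlap, stronger associations or the pooled sample it can be uncommon. The documents do not support saying that one hypothesis will be lost, or that it will be reported as refuted. They support saying that it may be left without an estimate. These are secondary hypotheses in an explorative study, so the change is advisable and does not affect the primary comparison.

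**What to change.** In section 10.5:

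1. Test H3 with the PHQ-9 change and H4 with the GAD-7 change, each in its own prespecified linear model of IBS-SSS change with the same small, fixed covariate set. Name the change scores explicitly, since 10.5 does not say whether baseline, follow-up or change is meant.
2. Report each estimate with its 95% confidence interval, whether or not AIC would keep the scale.
3. Add one model with both change scores to describe their joint contribution. Using this model alone would also give each hypothesis an estimate, but a conditional one.
4. Keep AIC selection as an exploratory description, and state that absence from the lowest-AIC model is not evidence of no association.

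The cost is a few sentences and a few regressions on data already being collected. The downside is that the separate anxiety and depression estimates overlap, so the report must say that they are not independent findings.

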Study population:	Nulliparous women with a diagnosis of PCOS who are eligible for IVF (in vitro fertilization) treatment with freeze-only strategy (i.e. deferred embryo transfer). Nulliparous women who embark on elective oocyte

	
cryopreservation. Both groups will receive PPOS (progestin-primed ovarian stimulation).

In- and exclusion criteria:	
Inclusion criteria PCOS group :
 
 - Diagnosis of PCOS according to the 2004 Rotterdam criteria - Initiating their first cycle of IVF treatment (PPOS and freeze only protocol) - Nulliparous - ≥ 18 years - Willing to participate in the study - Understanding Dutch, French or English 
Exclusion criteria PCOS group :
 
 - Known inflammatory bowel disorder - Known major intestinal bowel disorder - Known systemic or auto-immune disorder with implication for the GI system - History of abdominal surgery (appendectomy and cholecystectomy allowed if >6 months earlier) - History of gastro-enteritis in the past 6 weeks - Previous IVF treatment cycles 
Inclusion criteria social freezing group:
 
 - Initiating their first ovarian stimulation protocol for elective oocyte cryopreservation (PPOS and freeze only protocol) - Nulliparous - ≥ 18 years - Willing to participate in the study - Understanding Dutch, French or English 
Exclusion criteria social freezing group:
 
 - Diagnosis of PCOS - Known inflammatory bowel disorder - Known major intestinal bowel disorder - Known systemic or auto-immune disorder with implication for the GI system - History of abdominal surgery (appendectomy and cholecystectomy allowed if >6 months earlier) - History of gastro-enteritis in the past 6 weeks
Factors of interest / Data to be collected:	
IBS diagnosis and symptom severity Gastrointestinal symptom severity Depression levels Anxiety levels
 
Factors to be collected before ovarian stimulation:
 
 • Demographics (length, weight) • The duration of infertility • Obstetrical history: GPA (Gravida, Para and abortus) • The ethnicity • For the study group: the type of PCOS 
Factors to be collected after oocyte pick-up:
 
 • The hormonal profile at start and end of ovarian stimulation • The number of follicles on the last ultrasound before pickup • The number of COC (Cumulus-oocyte complex) collected during pick-up

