5.2 Types of PCOS

There are four types of PCOS. Phenotype A PCOS has ovulatory dysfunction, hyperandrogenism and polycystic ovarian morphology. Phenotype B PCOS has the same characteristics but without the polycystic ovarian morphology. These two phenotypes are considered the “classic PCOS”. Phenotype C is characterized by hyperandrogenism and polycystic ovarian morphology. It is also called the ovulatory PCOS. Phenotype D PCOS is also called non hyperandrogenic PCOS, it is characterized by ovulatory dysfunction and polycystic ovarian morphology. (7)

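### Section 10.5 selects baseline factors and the post-stimulation follicle count from one AIC pool, so associations under H7-H9 can be understated or dropped if they run through ovarian response.

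*Protocol*

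**What the plan says.** Protocol section 10.5 describes two regression models.

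- **Logistic model, IBS yes/no.** The candidate list reads: "The independent variables include GAD-7 score, PHQ-9 score, ethnicity, duration of the desire to have children, the number of follicles found on the US", and it trails off in an ellipsis. The selection rule is: "The model with the lowest AIC will be the final model". Of the IBS yes/no outcome, the section says "This answer will be defined before and after the fertility treatment"; it does not say which of the two statuses the model predicts.
- **Linear model, IBS-SSS change.** The list is illustrative: "independent variables (such as ethnicity, anxiety scores, duration of the desire to have children,...) have an influence on the score difference". Selection is again by AIC: "AIC will be used to evaluate the different possible models which will include different independent variables".

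The protocol summary in section 4 places the follicle count among the items collected after oocyte pick-up: "The number of follicles on the last ultrasound before pickup". Section 10.3 agrees that it comes from the final ultrasound.

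Section 6.2.1 states separate hypotheses for duration of infertility (H7), ethnicity (H8), PCOS phenotype (H9: "Among women with Polycystic Ovary Syndrome (PCOS), changes in IBS symptoms differ significantly according to PCOS phenotype"), hormonal profile (H10) and ovarian response on ultrasound (H11). Section 6.3 also plans before-and-after comparisons within subgroups formed by these factors.

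**The concern.** H7-H9 ask whether IBS symptoms or their change differ by a characteristic the woman has before stimulation starts. None of them is worded as holding ovarian response fixed, and H11 asks about ovarian response on its own. One final model cannot serve both kinds of question. Once the follicle count is in it, the coefficient of a baseline factor is what remains after the part passing through the ovaries has been removed.

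AIC makes this sharper. If the follicle count carries most of the signal, the baseline factor adds little to the fit and may be left out. The report could then call a factor unassociated although it does differ between women in the way the hypothesis states.

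This is separate from overfitting. It would remain with a fully pre-specified model and a large sample.

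**Working it through.** **1. Time order of the candidates.**

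| Variable | Fixed or measured | Named in logistic list | Named in linear list |
|---|---|---|---|
| Ethnicity | before stimulation | yes | yes |
| Duration of desire for children | before stimulation | yes | yes |
| PCOS phenotype | before stimulation | no | no |
| Hormonal profile | start and end of stimulation (section 4) | no | no |
| Follicle count | last ultrasound before pick-up | yes | no |

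The mixture is explicit in the logistic model, which bears on the prevalence part of H8. The linear list does not name the follicle count. However, H9-H11 concern change in IBS symptoms, and this is the only model of change in section 10.5. Unless phenotype, hormones and follicle count enter it, those hypotheses have no model there.

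**2. Is a path through ovarian response plausible?** For phenotype, yes. Section 5.2 defines the types partly by ovarian morphology: "Phenotype B PCOS has the same characteristics but without the polycystic ovarian morphology". Types A, C and D all have it, so the contrast is B against the rest. For ethnicity and duration, the protocol gives no such link.

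**3. Size.** The protocol states no power, alpha, SD or effect size. The only figure to reproduce is the sample size: 60 + 60 = 120, which agrees. Everything below is assumed:

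- two equal groups, n = 60 (30 v 30, the size of the PCOS group)
- total effect of the baseline factor 0.75 SD, within-group SD of the change score 1
- the factor shifts follicle count by a = 1 SD
- two-sided alpha 0.05
- share s of the effect passes through follicle count

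Formulas:

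- Direct effect = 0.75 × (1 − s). Follicle slope b = 0.75 × s / a.
- Standard error without follicle count = √(4/60) = 0.258, so the effect is 0.75/0.258 = 2.9 standard errors, giving power of about 0.81.
- Standard error with follicle count = 0.258 × √(1 − b²) × √1.25. The factor 1.25 is the variance inflation: 1 + a² × 0.25.
- Example, s = 50%: direct effect 0.375, b = 0.375, standard error 0.258 × 0.927 × 1.118 = 0.268. The ratio is 1.40 and power about 0.28.

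Simulation, 2,000 runs per row, choosing the lowest AIC among no predictor, factor only, follicles only, or both:

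| Share mediated | Mean adjusted coefficient | Power, no follicle count | Power, both in model | Power, lowest-AIC model | Factor dropped by AIC |
|---|---|---|---|---|---|
| 0% | 0.76 | 0.82 | 0.71 | 0.80 | 9% |
| 25% | 0.56 | 0.81 | 0.49 | 0.58 | 26% |
| 50% | 0.38 | 0.82 | 0.27 | 0.29 | 49% |
| 75% | 0.19 | 0.82 | 0.12 | 0.12 | 71% |
| 100% | 0.01 | 0.83 | 0.06 | 0.06 | 81% |

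The simulated 0.27 at 50% agrees with the formula.

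Doubling the sample (60 v 60) gives 0.97, 0.81, 0.51, 0.20 and 0.05 after AIC selection, against 0.98-0.99 without the follicle count. More patients do not rescue full mediation.

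A weaker shift, a = 0.5, at n = 60 gives 0.81, 0.60 and 0.55 for shares of 0%, 25% and 50%. Larger shares are not shown: at 75%, b = 0.75 × 0.75 / 0.5 = 1.125, so 1 − b² is negative and the assumed SD of 1 cannot hold.

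**The case against.** The strongest case is that section 10.5 does not doom H7-H9.

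- **The lists.** Phenotype and hormones are in neither list, and the linear list does not name the follicle count. A reader might infer that the plan puts all of them in one model of change; the text does not say so. What stands is that the list is open-ended and no other model of change is offered for H9-H11.
- **A second route.** Section 6.3 plans comparisons by duration, ethnicity and PCOS type with no adjustment for ovarian response. A reader might infer from section 10.5 alone that baseline effects are certain to be adjusted away; section 6.3 shows that this does not follow. But comparing before with after inside a subgroup does not test whether change differs between subgroups. No such test is stated, and nothing says which route decides if the two disagree.
- **Mediation is assumed.** This is correct. With no mediation the loss is 0.82 to 0.80, which is negligible. Only phenotype B lacks polycystic morphology, so the equal split and the 1 SD shift are illustrative. Morphology at diagnosis is also not the same as follicle count after stimulation.
- **Hormones.** The profile includes a start value, which stimulation does not produce. Only the end value raises this problem.
- **Pre-treatment status.** A reader might infer that follicle count will be used to predict IBS status before treatment. The sentence only says that status is recorded twice. It leaves that use open but does not state it.
- **Exploratory aim, and detail left to an SAP.** A mutually adjusted association model is legitimate in exploratory work, and allotting predictors to hypotheses often belongs in an SAP. But the protocol itself fixes the pooled list for the logistic model and the single-winner rule for both models.

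**Conclusion.** The point holds in limited form. Section 10.5 lets a post-stimulation variable compete with baseline factors in one search with one winner, explicitly for IBS status and by necessity for IBS-SSS change if that model is to serve H9-H11. An association under H7-H9 can therefore be understated or dropped. It is not shown that it will be.

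The size ranges from almost nothing (power 0.80 with no mediation) to near-total loss (0.06 with full mediation), against 0.81-0.83 without the follicle count at n = 60. The range rests on the assumed 0.75 SD effect, 1 SD shift, equal groups and 5% two-sided tests, and on a mediated share that the protocol does not give. PCOS phenotype is where the text makes the problem plausible; for ethnicity and duration it is only a possibility. The change is worth making because it costs almost nothing.

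**What to change.** In section 10.5, or in the SAP with a reference from it:

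1. Test H7-H9 in models with pre-stimulation variables only. Start-of-stimulation hormone values may be included.
2. Test H10-H11 in a separate model that adds the follicle count and end-of-stimulation hormones, adjusted for the baseline variables.
3. State that conclusions on H7-H9 come from the baseline-only models, and how the section 6.3 subgroup comparisons relate to them.
4. State that follicle count and end-of-stimulation hormones are not predictors in any model of pre-treatment IBS status.

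Cost: some wording and a few extra regressions on data already collected. No extra participants, visits or procedures are needed.
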